1 INTRODUCTION

This document is a clinical investigational plan for a human research study sponsored by Masimo Corporation. The study will be conducted in compliance with all stipulations of this protocol, ethical principles that have their origin in the Declaration of Helsinki, the conditions of IRB approval, applicable federal and local regulatory requirements, ISO-14155 and International Conference on Harmonization (ICH) E6 Good Clinical Practice (GCP) guidance.

1.1 Background and Rationale

The changes in intra-thoracic pressure associated with mechanical ventilation produce fluctuations in the venous return of blood to the heart and consequent changes in stroke volume. (Michard 2005) These dynamic changes can now be tracked by many invasive and non-invasive monitors based upon arterial pressure waveform analysis, ultrasound measurement of arterial flow or vena cava diameters, measurements of thoracic impedance or reactance and analysis of the pulse oximeter plethysmographic waveform. The magnitude of these variations can localize the patient's cardiac function on a classic Frank-Starling curve to guide therapy. Dynamic monitors of cardiac function provide a better prediction of the response of an individual patient to the administration of intravenous fluids when compared to the measurement of pressures within the cardiac chambers. (Marik 2009) Intra-operative optimization of fluid administration and cardiac function using these dynamic monitors decreases post-operative length of stay as well as peri-operative morbidity and mortality. (Gurgel 2011, Hamilton 2011)

Pleth Variability Index (PVi) (Masimo Corp., Irvine, CA, USA) is an algorithm built into the Masimo Radical 7 monitor that determines maximal and minimal plethysmographic waveform amplitudes and then calculates the percentage difference between the two providing a continuous assessment of the respiratory variations in the pulse oximeter waveform amplitude. Recently, Masimo has created a new parameter called RPVi, which is an enhanced version of the currently available PVi parameter. RPVi is available in the multi-wavelength rainbow sensors powered by rainbow® technology. Compared to PVi, RPVi may provide enhanced specificity to changes in fluid volume, a reduction in variability under certain conditions, and fewer post-dropout spikes. Different from other invasive dynamic indices, PVi provides clinicians with a numerical value noninvasively, automatically, and continuously (Sandroni 2012, Vos 2013, Zimmermann 2010). Similar to PVi, RPVi is calculated on the basis of perfusion index (Pi). The Pi value is generated by pulse oximetry and the scale of absorption of red and infrared light. Division of pulsatile fraction (AC, caused by blood flow) and non-pulsatile fraction (DC, effected by skin and other tissues) of the red and infrared light is summarized by the following formula:

$$Pi = (AC/DC) \times 100\%$$

RPVi reflects measurements of ventilation induced respiratory changes in Pi over a period of time and is calculated as follows:

$$PVi \text{ or } RPVi = [(Pimax - Pimin)/Pimax] \times 100(%)$$

Multiple studies have demonstrated that PVi can predict fluid responsiveness in mechanically ventilated patients (Desebbe 2010) and can be used to optimize intraoperative fluid therapy (Desebbe 2008). Yin and Ho (2012) and Sandroni (2012) have provided meta-analyses confirming the clinical utility of PVi to guide clinical care. Among the available dynamic monitors of cardiac function in common clinical use (pulse pressure variation PPV, stroke volume variation SVV, corrected esophageal Doppler flow time FTc, etc.) the respiratory variations in the pulse oximeter plethysmographic waveform amplitude (pleth variability index PVi) has the advantage of being completely non-invasive.

The sensitivity of a dynamic monitor of cardiac function is dependent on the magnitude of the swings in the intrathoracic pressure associated with mechanical ventilation. During the introduction of these monitors into daily anesthetic management there has been a concurrent evolution in our intra-operative ventilator management protocols. During the past decade of practice, commonly recommended intraoperative tidal volumes have declined from 10 ml/kg to 8 ml/kg and now down to 6 ml/kg. Recommendations for the use of dynamic monitors as a guide for intraoperative fluid management stress that positive studies were done with controlled tidal volumes of 8 ml/kg and their sensitivity has not been established under conditions

including smaller tidal volumes. There is a pressing need to re-evaluate the performance and utility of these monitors under currently recommended respiratory management practices.

The evolution of the pulse oximetry sensors to incorporate multi-wavelength technologies provided the opportunity to modify the PVi algorithm and improve clinical performance. As a dynamic monitor of cardiac function, PVi/ RPVi is analogous to pulse pressure variation (PPV), which may be derived through minimally-invasive means using beat-to-beat arterial pressure expressed as a percentage by the Philips IntelliVue (Philips Labs, Noord Brabant, NL) or stroke volume variation (SVV), which may be derived through minimally-invasive means using pulse contour analysis of the arterial pressure waveform as done by the Vigileo/Flotrac System (Edwards Labs, Irvine, CA) or Philips IntelliVue (Philips Labs, Noord Brabant, NL). Multiple studies have demonstrated that PPV and/or SVV is a valuable tool in predicting fluid responsiveness in mechanically ventilated patients.

The aim of this study is to test the ability of RPVi to predict fluid responsiveness in mechanically ventilated patients in the operating room and to compare it to other dynamic monitors of cardiac function in this setting.

This study will include patients [REDACTED] undergoing cardiac surgical procedures in which pulmonary and peripheral arterial catheters are standard monitors used for continuous monitoring of cardiac function and blood pressure, respectively. Patients with cardiac arrhythmias and intracardiac shunts will be excluded. Patients will be assigned to one of the two study groups with different tidal volumes: 6 ml/kg IBW and 8 ml/kg IBW. Both tidal volumes are within the range that is commonly used intra-operatively. In patients without significant pulmonary disease there is no significant risk or benefit associated with either tidal volume, however, there is evidence of decreased utility of the dynamic monitors of cardiac function (PPV/SVV) at lower tidal volumes. Attention to the tidal volume will aid the assessment of the utility of RPVi as a monitor of cardiac response to fluid administration.

1.2 Investigational Device

Masimo Rainbow technology uses a multi-wavelength sensor with various LEDs that pass light through the measurement site to a diode (detector) as shown in the figure below. Signal data is obtained by passing various visible and infrared lights through a capillary bed (for example fingertip) and measuring changes in absorption during the blood pulsatile cycle. The detector receives the light and converts it to an electrical signal which is, in turn, used to predict various parameters.

[figure not shown]

Figure 1: Masimo Rainbow technology overview

Devices used for RPVi evaluation consist of a Masimo Rainbow portable handheld pulse co-oximeter that is docked to a Masimo Root Patient Monitoring and Connectivity Platform and connected to a sensor that can measure SpHb, RPVi, SpO₂, pulse rate (PR) and perfusion index (Pi). Masimo Rainbow pulse CO-oximeters are a non-significant risk device that has no additional risks compared to the commercially available pulse CO-oximeter devices.

The Masimo Rainbow sensors are constructed of a soft, flexible polymer in which LED emitters and photodiode detectors are embedded. The sensors, including the LED, photodiodes are the same as that used by commercially available pulse oximeter sensors.

Investigational devices to be used in this study are: Masimo CO-Oximeter devices and non-invasive prototype sensors equivalent to the FDA-cleared sensors; investigational devices and sensors similar in design, material, and risk to Masimo

FDA-cleared products that may be placed on the fingers, shielded from outside light, and attached to the Masimo monitor. The sensors along with its associated devices measure non-invasive physiological parameters like hemoglobin (SpHb), Pulse Rate (PR), Perfusion Index (Pi), Methemoglobin (SpMet), Pleth Variability Index (PVi), RPVi, etc.

1.3 Risk/Benefits

Benefits: There is no specific benefit to the individual subjects for participation in this research protocol.

Sensor risks: As with all optical sensors, the investigational device has the risk of thermal burn. Pulse CO-oximeter noninvasive measurement uses wavelengths in the red and near infrared range like a conventional pulse oximeter used in routine clinical practice for over 15 years. The additional LEDs from Rainbow sensors have been tested and meet the Exempt classification for photo-biological safety of light sources.

All patient-contact materials, including the adhesive used in the design of the Masimo Rainbow sensors, have been subjected to biocompatibility tests per ISO 10993-1 and results demonstrate that the materials are non-toxic, non-irritating, and non-sensitizing. The sensors have been subjected to performance, mechanical, and electrical testing and results demonstrate that the sensors meet the requirements for safety and effectiveness for the intended use of the product.

No other physical, financial, social or psychological risks are anticipated to be associated with participation in this study. Precautions taken to safeguard protected personal health information are described in **section 4.4** on recruitment. The risks associated with the anesthetic and surgical procedure are not discussed in this protocol.

2 STUDY OBJECTIVES

2.1 Primary Objective

This is a prospective, nonrandomized, sequential data collection study to evaluate the ability of RPVi to predict fluid responsiveness in comparison with other dynamic parameters including SVV and/or PPV. Although this is a non-interventional study, focused on data collection, patients will be assigned to one of the two study groups with different tidal volumes: 6 ml/kg IBW and 8 ml/kg IBW. The research data will not be used to modify the subject's standard of care.

Specific aims:

- Evaluate the clinical utility of the RPVi as a predictor of fluid responsiveness in mechanically ventilated patients at two specific tidal volumes (6 ml/kg IBW and 8 ml/kg IBW).
- Characterize the correlations between the RPVi and PPV and/or SVV, as measured by FDA cleared comparator systems, as predictors of fluid responsiveness at two specific tidal volumes (6 ml/kg IBW and 8 ml/kg IBW).

Hypothesis (constructed as the null):

- RPVi as a dynamic monitor of cardiac function will not predict a subsequent increase in cardiac output following the administration of a fluid bolus of a crystalloid solution at a tidal volume of either 6 or 8 ml/kg IBW in intubated, mechanically ventilated patients.

- Changes in RPVi will not differ from concurrent changes in PPV and/or SVV, as measured by FDA cleared comparator systems following the administration of a fluid bolus of a crystalloid solution at a tidal volume of either 6 or 8 ml/kg IBW in intubated, mechanically ventilated patients.

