4 SUBJECT SELECTION AND WITHDRAWAL

4.1 Number of Subjects

There will be up to 150 subjects enrolled into this study, divided into two groups. There will be no protocol or procedural differences between the groups. The first group of up to 100 subjects will be used to gather data to determine the thresholds for fluid responsiveness that would be used for the second group of 50 subjects. The second group will be the validation set to be used to evaluate study objectives. The anticipated duration of subject participation in this study will not exceed 1 visit. The study enrollment period is expected to be approximately 2 years.

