7 STUDY PROCEDURES

- Patients are assigned to be ventilated in a volume controlled mode with a tidal volume of either 6 or 8 $\text{ml} \cdot \text{kg}^{-1}$ of ideal body weight (Devine formula) at a frequency [REDACTED]. Positive end-expiratory pressure is to be set [REDACTED] according to the attending physician.
- Anesthesia is induced as per standard of care. Radial and pulmonary arterial catheters inserted as per standard of care.
- All required sensors are placed as per the corresponding instructions for use for the various measurements
- All patients are to be studied [REDACTED] with no changes in anaesthetic protocol and no volume expansion. Unless clinically contraindicated, patients will receive an intravenous volume expansion consisting of [REDACTED] given over [REDACTED].
- Baseline set of haemodynamic measurements (stroke volume and or cardiac output) are to be performed prior to the intravenous volume expansion.
- A repeat set of hemodynamic measurements are to be performed [REDACTED] after volume expansion.

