8 STATISTICAL PLAN

Prior studies of the predictive abilities of dynamic monitors of cardiac function with respect to cardiac output have established that sample sizes of 50 patients are sufficient to characterize the performance of the monitor. However, based on an ongoing Masimo study at another clinical test site, preliminary data received suggests that, of the first 83 subjects enrolled approximately 29% were responders. Therefore, in order to analyze the ability of RPVi, the sample size will be increased to a total of up to 150 patients. The first group of up to 100 subjects will be used to gather data to determine the thresholds for fluid responsiveness that would be used for the second group of 50 subjects. The second group will be the validation set to be used to evaluate study objectives in **section 2.1**. As such, the study will be registered on ClinicalTrials.gov but only results from the validation phase will be posted.

Normality of distribution will be tested before any statistical evaluation by using the Kolmogorov- Smirnov method. Descriptive statistical data will be reported as mean \pm SD. Except for the bias between both methods (RPVi vs PPV/SVV and SV/CO measurements). Comparisons between PPV/SVV and RPVi and between CO/SV measurements will be performed with a paired student t test. PPV/SVV and RPVi as well as SV/CO measurements will be compared using Bland and Altman. In order to evaluate the ability of RPVi to reliably detect changes in PPV/SVV and for CO measurements to accurately track Flotrac CO changes we will use a method based on polar plotting of PPV/SVV and RPVi and CO measurements changes over consecutive cycles as described by Critchley et al. We will exclude from this analysis small changes of mean value of

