PPV/SVV and RPVi and CO measurements less than 3%. In this method, a good trending ability requires an angular bias no greater than ± 5 degrees and a SD for the polar angle of less than ± 15 degrees. In this method, simultaneous changes of each indices of consecutive validated respiratory cycle will be reported on a polar plot. The polar angle will be derived from the ratio of the changes of the two indices such a ratio close to one led to a null angle with the x axis, this angle approach a 90 degrees angle when the ratio diverges from one. The radius will be the mean of the simultaneous changes of the two indices between two consecutive validated respiratory cycles. In these conditions a mean angle and its SD can be calculated.

The strength of linear dependence between PPV/SVV and RPVi and SV/CO measurements for all patients will be measured by the Pearson coefficient of correlation. The mean of correlation coefficients and comparison between correlation coefficients will be performed after a Fischer's transformation. In order to analyze the ability of RPVi to correctly classify the respiratory cycle as responder or non-responder after a volume loading in respect to a theoretical threshold value of PPV/SVV of 12%, we will measure the area under the curve of a Receiver Operating Characteristic (ROC) curve. Then the selected value of RPVi for each patient will be the one which maximized the Youden index (sensitivity + (specificity - 1)). The agreement between the two classifications will be quantified by the Kappa score for each patient, taking as threshold value of RPVi the individual value determined by the ROC curve. The reported mean values of areas under ROC curves and Kappa scores will be therefore calculated from the individual values. Taking the intra patients coefficient of correlation as a dependent variable, we will estimate its relationship with potentially explanatory variables by using univariate analysis, including Student t test for qualitative data and correlation for quantitative data and multivariate analysis by multiple linear regression. Categorical binary variable will be transformed into dummy variables. Other correlations will be evaluated by Pearson coefficient.

For all comparisons, a P value < 0.05 will be considered significant. Statistical analysis will be performed using SPSS software version 13.0 for Windows (SPSS Inc., Chicago, IL).

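### Hypothesis 1 concerns a rise in cardiac output, but sections 7 and 8 let stroke volume stand in for it and the only ROC rule uses a third reference, so response is not one fixed outcome

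*Combined protocol and SAP*

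**What the plan says.** Four places in the protocol bear on what counts as a response.

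- **Section 2.1.** The first null hypothesis is that RPVi "will not predict a subsequent increase in cardiac output following the administration of a fluid bolus". The variable is CO; no size of increase is given.
- **Section 7.** "Baseline set of haemodynamic measurements (stroke volume and or cardiac output) are to be performed prior to the intravenous volume expansion". After the bolus, "A repeat set of hemodynamic measurements are to be performed", and the visible text does not name the variable. SV alone, CO alone or both would comply.
- **Section 8, method comparison.** "PPV/SVV and RPVi as well as SV/CO measurements will be compared using Bland and Altman". SV and CO appear as a pair throughout, and nothing says which decides response.
- **Section 8, ROC analysis.** RPVi is to classify respiratory cycles as "responder or non-responder after a volume loading in respect to a theoretical threshold value of PPV/SVV of 12"%. That reference is neither SV nor CO.

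Section 4.1 uses the first group (up to 100) to "gather data to determine the thresholds for fluid responsiveness that would be used for the second group of 50 subjects", without naming the variable behind those thresholds. Section 8 reports that at another site "of the first 83 subjects enrolled approximately 29% were responders", again without naming a variable or cut-off.

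**The concern.** SV and CO are different outcomes. CO is SV multiplied by heart rate, so their percent changes agree only when heart rate is the same before and after the bolus. This holds even if one monitor supplies both.

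Two gaps follow. A patient with SV only complies with section 7 but has no outcome under hypothesis 1 unless SV is substituted, which no rule permits or forbids. A patient with both has two possible labels and no order of precedence, so the choice can be made once the results are known. In a study that sets thresholds in one group and validates them in another, the outcome variable is one of the things that should be fixed before the second group is analysed.

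The ROC rule does not close the gap. Its reference is a dynamic index before or after loading, so an ROC against it does not test whether RPVi predicts a rise in CO.

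**Working it through.** **Inputs from the documents.** Outcome in hypothesis 1: CO (section 2.1). Variables measured: SV and/or CO (section 7). Groups: up to 100 plus 50 = 150 (sections 4.1 and 8). Responder rate at the other site: about 29% of 83, that is 0.29 x 83 = 24.1 subjects (section 8). Applied to the validation group, 0.29 x 50 = 14.5 responders.

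The documents give no power, target AUC or precision, so the figure of 150 cannot be reproduced beyond that addition. They also give no heart-rate change, no SV change and no cut-off for a rise in CO or SV. Everything below that uses such values rests on assumptions.

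**Identity.** CO change = (1 + SV change) x (1 + heart-rate change) - 1.

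**Single patients (assumed values).**

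| Cut-off | SV change | Heart-rate change | CO change | By SV | By CO |
|---|---|---|---|---|---|
| Any rise | +3% | -5% | 1.03 x 0.95 - 1 = -2.2% | yes | no |
| 10% | +12% | -5% | 1.12 x 0.95 - 1 = +6.4% | yes | no |
| 10% | +8% | +3% | 1.08 x 1.03 - 1 = +11.2% | no | yes |

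With heart rate down 5%, SV must rise 1.10/0.95 - 1 = 15.8% for CO to reach +10%, and 1.15/0.95 - 1 = 21.1% for CO to reach +15%. The disagreement runs in both directions and does not depend on a particular cut-off.

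**Everyone switched from SV to CO (simulation).** Normal SV and heart-rate changes were drawn, the mean SV change was set so that 29% respond by SV, and patients whose two labels differ were counted. The 29% is only a calibration point; the plan does not say that its responders were defined by SV. Cut-offs were 10% and 15%.

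| SD of SV change | Heart-rate change | Labels differ | Of 50 |
|---|---|---|---|
| 12% | mean 0, SD 1-2% | about 2.5-5% | about 1-3 |
| 8-15% | mean 0 to -5%, SD 3-5% | 5.9-18.8% | 3.0-9.4 |
| 12% | mean -6%, SD 6%, correlation -0.3 with SV change | 19-20% | about 10 |

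In the middle row the CO responder rate runs from 14.5% to 32%, against 29% by SV. If heart rate does not change, the labels agree.

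**A mixture.** If CO is the outcome and SV is substituted only where CO is missing, the share mislabelled is (share with SV only) x (share whose labels differ). With an assumed 20% SV-only and 10-20% differing: 0.20 x 0.10 = 2% to 0.20 x 0.20 = 4%, or 1 to 2 of 50.

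**The case against.** The strongest reply is that CO will be available in practice. Sections 1.1 and 7 describe pulmonary arterial catheters as standard, section 8 speaks of tracking FloTrac CO, and section 1.2 lists pulse rate among the study sensor's outputs, so CO could be rebuilt from SV. The SV-only patient may be rare. That stands, and it limits the size of the problem. It does not settle which variable decides when both exist, and it makes the remedy nearly free.

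Some stronger readings are tempting but unsupported.

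- *The planned AUC, sensitivity and specificity shift with SV or CO.* The only ROC analysis written in section 8 uses PPV/SVV of 12% and would not change. The fault is that this analysis does not address hypothesis 1.
- *With about 14.5 responders, each reclassified patient moves sensitivity by about 7 points.* Reclassification changes the denominator too. From an illustrative 12/15 (80.0%), losing a detected responder gives 11/14 = 78.6%, losing a missed one 12/14 = 85.7%, gaining a detected one 13/16 = 81.3%, and gaining a missed one 12/16 = 75.0%.
- *The plan's 29% is an SV rate, so CO would yield fewer responders than planned.* Section 8 does not attribute the 29% to either variable.
- *The SV/CO mix will differ between the two groups.* Section 4.1 says procedures are the same in both. The shared procedure permits either variable, but nothing shows that the mix will differ.

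Part of section 7 is redacted and some protocol text was not available, so a fuller responder definition cannot be excluded. The visible wording of sections 2.1, 7 and 8 would still need to be brought into line with it.

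**Conclusion.** The point holds as an inconsistency in the outcome variable: CO in the hypothesis, SV and/or CO in the procedures, SV/CO in the statistical plan, and PPV/SVV in the only ROC rule. Hypothesis 1 has no outcome in an SV-only patient, and the choice is open after the fact when both are recorded. It would be too strong to say that hypothesis 1 already defines a responder, since it names a variable without a cut-off.

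The number affected cannot be derived from the documents. About 6-20% of patients would change class if all were switched from SV to CO, under assumed heart-rate SDs of 3-6%, and about 2.5-5% if heart rate is very stable. Those figures are for a wholesale switch; a mixture would affect fewer. This should be corrected before the validation group is analysed, but the documents do not show that a result would be overturned.

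**What to change.** 1. **Section 7.** Require CO, SV and heart rate at both the baseline and the repeat measurement. Where a monitor outputs only SV, compute CO as SV x simultaneous heart rate.
2. **Section 8, response.** Define response for every patient as the percent change in CO from baseline to the repeat measurement, in line with hypothesis 1. State one cut-off, fixed before the validation group is analysed.
3. **Section 8, ROC.** Run the ROC and Youden analysis for hypothesis 1 against that CO response, across patients because each has one response. Keep the PPV/SVV 12% classification only as a separate agreement analysis.
4. **Sensitivity analysis.** Report SV-defined response under that name.

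The cost is wording in the protocol and statistical plan. No patient or procedure is added, because pulse rate is already among the study sensor's outputs. The downside is that the CO-based responder count may differ from the 29% used for planning, so the expected 14.5 responders among the 50 should be treated as uncertain.
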